**Enhanced Medical Rehabilitation in Older Adults (EMR R01)
Statistical Analysis Plan (Final)**

Trial Registration Number: NCT02114879

SAP Version: 2

Version Date: 5/29/2019

Protocol Version: 8

Roles and Responsibilities

[name] MS; SAP Author
[name] AB; Senior Biostatistician
[name]; Principal Investigator
[name] PhD; Co-Investigator
[name], MSW; Study Coordinator

Abbreviations:

EMR: Enhanced Medical Rehabilitation

SOC: Standard of Care

SNF: Skilled Nursing Facility

OT: Occupational Therapy

PT: Physical Therapy

PI: Principal Investigator

AE: Adverse Event

SAE: Serious Adverse Event

MADRS: Montgomery and Asberg Depression Rating Scale.

CIRS-G: Cumulative Illness Rating Scale for Geriatrics

SBT: Short Blessed Test

SAS: Statistical Analysis Software

ANCOVA: Analysis of Covariance

Introduction:

- i. Background and Rationale:

Americans are aging and having more medical events such as heart attack, stroke, and hip fracture. More than ever, older adults are surviving these events and leaving the hospital, alive but severely disabled. The solution for these highly disabled older adults is rehabilitation in the post-acute care setting, a large and rapidly-growing sector of care. Post-acute rehabilitation consists of daily physical therapy (PT) and occupational therapy (OT) to achieve restoration (e.g., regain walking ability and counteract bone and muscle loss by gait and muscle strengthening exercises), and adaptation (e.g., learn to perform activities of daily living and safely live at home). The most common setting for post-acute rehabilitation is a skilled nursing facility (SNF). Length of stay is about 3 weeks, a narrow window in which to recover and return home or be institutionalized.

Post-acute rehabilitation is low-intensity, low-engagement and too often fails to achieve functional recovery, especially in the most vulnerable individuals. This problem should be remediable by applying the science of behavior change to this setting. We therefore developed Enhanced Medical Rehabilitation.

ii. Objectives:

1. Aim 1 (Primary): Examine the effectiveness of EMR for improving functional outcomes in older adults admitted to SNFs for post-acute rehabilitation.

H1: EMR will improve functional recovery to a greater extent than standard-of-care rehabilitation.

Explanation: The purpose of H1 is to examine the effectiveness of EMR. If H1 is supported, this could establish EMR as the gold-standard practice for post-acute rehabilitation. Our primary analysis is the change from baseline to Discharge. This single primary endpoint allows for an effectiveness test that is not confounded by length of stay differences or post-discharge issues beyond the reach of EMR.

2. Aim 2: Examine EMR's ability to overcome patient-level barriers to successful rehabilitation.

H2: The effectiveness of EMR for functional recovery will be greatest in: (a) patients with clinical depression; (b) patients with high levels of medical comorbidity; (c) patients with cognitive impairment.

Explanation: EMR was designed to overcome barriers to rehabilitation (for example, due to depression); therefore, the difference in functional recovery between EMR and SOC should be greater in the most vulnerable older adults. If H2 is supported, we will demonstrate that older adults with these common comorbidities benefit the most from high intensity, high engagement rehabilitation. If so, this would refute conventional wisdom in post-acute rehabilitation, codified in admission criteria for rehabilitation facilities, regarding the appropriate candidates for rehabilitation (as described in Significance).

3. Aim 3 (Secondary): Effect of EMR on MADRS scores on individuals with clinical depression.
4. Calculated a rate of clinical depression (SCID for those with elevated MADRS score):

22 participants had the SCID administered.

8 did not have depression diagnosis while 14 did have depression diagnosis.

Conclusion: only 14 individuals in the study had a clinical depression (ie, a diagnosis of depression). No further analyses to be done.

Additional Variables/Outcomes

6-Minute Walk/Gait Speed: Administered at Baseline and Discharge. Two components for 6-Minute Walk:

- 1) Distance Ambulated (feet): text box. If unable to complete, distance was entered as a 0.
- 2) Time: options are 6 minutes, Other time (MM:SS), and N/A

Two components for Gait Speed (Baseline, Day 30, Discharge):

- 1) Distance: radio button (10 meters, 4 meters, 0 meters). If unable, 0 meters selected.
- 2) Time (seconds): text box (if unable, time is 0).

Disposition (i.e., discharge to community vs. not)

Rehospitalization (rate).

Secondary analyses (not for main paper):

1. PANAS (A positive and a negative affect score).
2. PROMIS (Ability to Participate in Social Roles and Activities).
3. OARS IADL.

Process data: Measures of the dosage of intervention (# of EMR steps done in each therapy activity; PAT %; Rehab Participation Scale Score) before and after training.

Study Methods:

i. Trial Design:

This was a randomized, parallel-group trial where patients received either EMR or SOC therapy.

Patients who received EMR received therapy only from therapists who were trained and supervised in EMR. Their therapy sessions followed the EMR protocol. Otherwise, their SNF care did not differ from usual care.

Patients who received SOC received therapy only from PT/OTs (or assistants) who were not trained nor supervised in EMR. These therapists were monitored (videotaped or observed) but were not asked to do anything differently with their patients.

ii. Randomization:

Randomization (blocks...2 and 4 patients). was 1:1 to EMR or SOC with stratification by SNF site and by baseline depression status.

iii. Sample Size:

The sample size was based on 80% power to detect a Cohen's $d=0.4$ effect size on the ANCOVA difference in treatments at primary endpoint, based on a two-tailed $p<0.025$ (because two outcome measures are used). G*Power 3.1.2 was used for power calculations. A Cohen's $d=0.4$ is between "small" (0.2) and "medium" (0.5) effect sizes. Effect sizes for function were in the "large" range, $d=0.7-0.9$, but we acknowledge that these observed effect sizes are qualified by the small sample size, and it makes most sense to be more cautious regarding likely effect sizes in a full-scale study, hence our choice to power at $d=0.4$. Such an effect size is clinically relevant for the functional outcomes. *We will only examine affective recovery as an outcome for those who are "affectively impaired" to begin with; i.e., those with clinical depression at baseline; with this reduced N, we are powered at 80% for a $d=0.54$. This same power analysis would apply for any subgroup analysis of depressed; i.e., if we wish to demonstrate that EMR is effective both in the case of clinical depression and in "non-depressed" older adults.*

iv. Statistical Interim Analyses/Stopping Guidance:

Not applicable; we did not have any interim data analysis or early stopping plans.

v. Timing of Final Analysis:

All outcomes will be analyzed collectively.

vi. Timing of Outcome Assessments (including windows):

	Schedule of Assessments	SNF admit (baseline)	Day 7	Day 30	SNF discharg e	Day 60	Day 90
Outcomes	Function						
	Barthel Index (primary outcome)	X		X	X	X	X
	Gait speed	X		X	X		
	6-minute walk	X			X		
	Depression SCID (given if indicated by MADRS)	X					
	MADRS	X		X			
	17-item positive and negative affect scale	X	X	X		X	X

Processes	Rehabilitation intensity					
	Patient active time & actigraphy (at 20% of sessions at random)	collected each session throughout stay				
	Treatment engagement					
	Observer-rated Rehabilitation Participation Scale (at 20% of sessions at random)	collected each session throughout stay				
	Fidelity data (at 20% of session at random)	collected each session throughout stay				
	Post-Treatment Affect					
	Self-Assessment Moniker (at 20% of session at random)	collected each session throughout stay				
	Patient Satisfaction and Treatment Fidelity Survey	Collected after therapy sessions				
	Other rehabilitation variables					
	Rehospitalization		X	X	X	X
	Disposition (home, long-term care)	X	X	X	X	X
	Social Participation (PROMIS Ability to Participate in Social Roles and Activities)				X	X
	Instrumental Activities of Daily Living (OARS IADL)				X	X
	Executive Functioning (Clock Drawing Test)	X				
	Fear of Falling	X				
	Readiness for Rehab	X	X			
	Short Blessed Test	X				
	Medical Comorbidity (CIRS-G)	X				
	Barthel Index: Pre-morbid version	X				

Statistical Principles:

i. Confidence Intervals and P-Values

Level of significance is 5%

ii. Adherence and protocol deviations

Protocol Deviation:

Any alteration or modification to the IRB-approved research without prospective IRB approval. The term research encompasses all IRB-approved materials and documents including the detailed protocol, IRB application, consent form, recruitment materials, questionnaires/data collection forms, and any other information relating to the research study.

Therapist adherence and competence was tracked two times per participant.

Variables: number of EMR principles used per therapy session; PAT.

iii. Analysis Populations

Trial Population:

- i. Screening data to describe representativeness of trial sample will include age, gender, race and ethnicity.
- ii. Eligibility

Inclusion Criteria:

- a. 65 years of age and older
- b. Admitted to a skilled nursing facility for post-acute care from PT and OT for 2 weeks or more.

Exclusion Criteria:

- a. Language, visual or hearing barriers to participation (e.g. unable to communicate with research staff).
- b. Medical illness preventing study participation or accurate data collection (e.g., highly unstable cardiac illness such that early re-hospitalization is expected; metastatic or other cancer such that hospice is recommended or survival is limited).
- c. Moderate-severe dementia (demonstrated by chart diagnosis and/or short blessed score greater than 13).
- d. Progressive neurological condition such that recovery of function is not feasible.
- e. Patient did not have the ability to walk prior to hospitalization (e.g. paraplegic).
- f. Schizophrenia or other chronic or current psychotic disorder.
- g. Patient normally resides in a long-term care facility.

- iii. Recruitment: the numbers that will be presented in a CONSORT diagram include:
 - 1. # Screened/Consented and reasons for ineligibility.
 - 2. # Randomized to EMR vs SOC.
 - 3. # Present at each follow-up time point (i.e., Day 30, Discharge, Day 60, and Day 90); reasons for discontinuation/lost to follow-up.
 - 4. # Included in Final Analysis; reasons excluded from final analysis.
- iv. Withdrawal/follow-up

No follow-up was done for withdrawn participants. If a participant was withdrawn, then an attempt was made to obtain final prognosis information using clinical data available from the chart unless explicitly told not to do so by the participant.

v. Baseline Patient Characteristics

In addition to the screening variables described above, the variables below will also be summarized in a Baseline Characteristics Table. Continuous variables will be summarized using median and IQR while categorical variables will be summarized using counts and percentages. These statistics will be provided by condition (EMR Vs SOC) and as a whole.

- Barthel Index
- MADRS Score
- Gait Speed (Distance in meters and Time in seconds)
- 6-Minute Walk (Distance Ambulated, in feet)
- PANAS Score
- Short Blessed Test Score
- CIRS-G Score
- Clock Drawing Score

Analysis:

i. Outcome Definitions

- 1) Aim 1: Examine the effectiveness of EMR for improving functional outcomes in older adults admitted to SNFs for post-acute rehabilitation.

H1: EMR will improve functional recovery to a greater extent than standard-of-care rehabilitation.

The primary measure employed for assessing functional improvement will be The Barthel Index. This index is a 10-item scale used to ascertain the degree of independence of normal daily activities. This will be done by taking the sum of these 10 items. A high score indicates a high degree of independence, and a score can range from 0 to 100.

- 2) Aim 2: Examine EMR's ability to overcome patient-level barriers to successful rehabilitation.

H2: The effectiveness of EMR for functional recovery will be greatest in: (a) patients with clinical depression; (b) patients with high levels of medical comorbidity; (c) patients with cognitive impairment.

Part (a) will be assessed using the MADRS, which is a 10-item scale used to assess for major depression. Each item is rated on a scale of 0 to 6, where a 6 is worse. The total score (i.e., sum of these 10 items) will be

used to assess for major depression and can range from 0 to 60.

Part (b) will be assessed using the CIRS-G, which is a 13-item scale used to assess for disease in all major body systems. Each item is rated on a scale of 0 to 4, with a 4 indicating severe impairment. The total score (i.e., sum of these 10 items) will be used to assess for medical comorbidity and can range from 0 to 52.

Part (c) will be assessed using the SBT Scores. The SBT is a 6-item scale used to assess for memory/concentration deficits. A total score, which is obtained after applying a weighting factor to each item then summing up the final item scores, can range from 0 to 28. A high score indicates impairment consistent with dementia.

ii. Analysis Methods

The primary outcome analysis for functional recovery will use a marginal model with time (baseline and discharge), condition (E-MR vs. SOC) and time x condition as fixed effects and with a covariance structure specified based on the Bayesian Information Criterion (BIC). Employing a marginal model allows for a more robust approach in the handling of missing data compared to the traditional ANCOVA model.

For H2 under Aim 2, each potential continuous moderator will be individually inserted into the primary model. The term of interest will be the time x condition x moderator interaction.

The secondary analyses for Six-Minute Walk distance and Gait Speed will use a Mann-Whitney U Test to test for differences in means between groups. In addition, a Chi-Square test will be employed to test for independence between condition and the secondary outcome variable re-hospitalization. Finally, the outcome of self-reported function will use a marginal model using time (30, 60, and 90 days), condition and time x condition as fixed effects, with a covariance structure specified based on BIC.

Exploratory analyses will also test whether the effects of age, gender, race and site (i.e., Barnes Jewish Extended Care Vs Alexian Brothers Sherbrooke Village) altered the conclusions of the primary results as well as the conclusions of the moderator results.

Note: we will not look at the nesting of subjects within therapists who are then nested within site as this is not possible due to the inconsistency of assigning therapists to participants.

iii. Missing Data

We use a marginal model which accounts for missing data (no multiple imputation was used).

iv. Harms

An adverse event (AE) is any untoward medical occurrence in a subject temporally associated with participation in the clinical study or with use of the experimental agent being studied. An adverse finding can include a sign, symptom, abnormal assessment (laboratory test value, vital signs, electrocardiogram finding, etc.), or any combination of these.

AEs will be labeled according to severity (i.e., mild, moderate or severe), which is based on the AE's impact on the participant.

AEs will be categorized according to the likelihood that they are related to the study intervention or other study procedures (i.e., definitely unrelated, definitely related, probably related, or possibly related).

SAEs that are unanticipated, serious, and possibly related to the study intervention will be reported to the IRB, and NIMH in accordance with requirements. Unexpected fatal or life-threatening AEs related to the intervention will be reported to the NIMH Program Officer within 7 days. Other serious and unexpected AEs related to the intervention will be reported to the NIMH Program Official within 15 days. Anticipated SAEs will be handled in a less urgent manner but will be reported to the IRB in accordance with their requirements.

v. Statistical Software

All analyses will be performed using SAS and/or R.

vi. References

none

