H1: EMR will improve functional and affective recovery to a greater extent than standard-of-care rehabilitation.

Explanation of H1: The purpose of H1 is to examine the effectiveness of EMR. If H1 is supported, this could establish EMR as the gold-standard practice for post-acute rehabilitation. Our primary analysis is the change from baseline to Day 30. This single primary endpoint allows for an effectiveness test that is not confounded by length of stay differences or post-discharge issues beyond the reach of EMR.

C2 Secondary Aim

Aim 2: Examine EMR's ability to overcome patient-level barriers to successful rehabilitation.

H2: The effectiveness of EMR for functional recovery will be greatest in: (a) patients with clinical depression; (b) patients with high levels of medical comorbidity; (c) patients with cognitive impairment.

Explanation of H2: EMR was designed to overcome barriers to rehabilitation (for example, due to depression); therefore, the difference in functional recovery between EMR and SOC should be greater in the most vulnerable older adults. If H2 is supported, we will demonstrate that older adults with these common comorbidities benefit the most from high intensity, high engagement rehabilitation. If so, this would refute conventional wisdom in post-acute rehabilitation, codified in admission criteria for rehabilitation facilities, regarding the appropriate candidates for rehabilitation (as described in Significance).³²

C3 Rationale for the Selection of Outcome Measures

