The results of this research may benefit society in that it will lead to an intervention which addresses a major gap in medical/functional rehabilitation in an acute rehab setting.

2.f Early Withdrawal of Participants

Participants may be withdrawn prior to study completion for a variety of reasons. Reasons for withdrawal will be noted on a termination form. There are no risks associated with early withdrawal. Common reasons for early withdrawal include:

- Screen failures: (note which exclusion criteria was met)
- Participant withdraws from study: (note the participant's stated reason for withdrawing)
- Participant no longer able to comply with protocol: (note reason)
- Death: (note date of death and source of information)

2.g Data Collection and Follow-up for Withdrawn Participants

During a situation where a participant is unable to be interviewed due to incapacitation or death of participant, research staff will attempt to collect final prognosis information from participant's medical chart or by asking a family member.

Research staff will collect no further data from screen failures. Withdrawn participants will not otherwise be followed up with.

F Study Procedures

F1 Screening for Eligibility

Upon receiving notification of a newly admitted patient to Barnes-Jewish Extended Care, research staff will review patient for information related to eligibility criteria. If the patient appears to be eligible, they will be screened using the Short Blessed Test (see 2.c.).

F2 Schedule of Measurements

Prior to meeting with a participant to perform study assessments, study staff will check-in with facility patient-care staff to confirm the availability of the participant. To ensure participants' comfort, the study team will assess the setting and ensure that the individual is positioned such that they can comfortably complete any assessments, including writing in a reasonable position, that they have had an opportunity to go to the toilet, eat and are dressed (if appropriate). Just asking the participant may not be the best approach for all individuals as some may agree without actually feeling this it is the best time or situation. It is important that participants not put off their own needs (whether it be repositioning themselves, using the bathroom or getting dressed) and that the research assessments not interfere with this.

	Schedule of Assessments	SNF admit (baseline)	Day 7	Day 30 (primary endpoint)	SNF discharge	Day 60	Day 90

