Outcomes	Function						
	Barthel Index (primary outcome)	X		X	X	X	X
	Gait speed	X		X	X		
	6-minute walk	X			X		
	Depression SCID (given if indicated by MADRS)	X					
	MADRS	X		X			
	17-item positive and negative affect scale	X	X	X		X	X
Processes	Rehabilitation intensity						
	Patient active time & actigraphy (at 20% of sessions at random)	collected each session throughout stay					
	Treatment engagement						
	Observer-rated Rehabilitation Participation Scale (at 20% of sessions at random)	collected each session throughout stay					
	Fidelity data (at 20% of session at random)	collected each session throughout stay					
	Post-Treatment Affect						
	Self-Assessment Moniker (at 20% of session at random)	collected each session throughout stay					
	Patient Satisfaction and Treatment Fidelity Survey	Collected after therapy sessions throughout stay					
	Other rehabilitation variables						
	Rehospitalization			X	X	X	X

Disposition (home, long-term care)	X		X	X	X	X
Social Participation (PROMIS Ability to Participate in Social Roles and Activities)					X	X
Instrumental Activities of Daily Living (OARS IADL)					X	X
Executive Functioning (Clock Drawing Test)	X					
Fear of Falling	X					
Readiness for Rehab	X	X				
Short Blessed Test	X					
Medical Comorbidity (CIRS-G)	X					
Barthel Index: Pre-morbid version	X					

F3 SNF Admit (Baseline) Visit

The baseline visit will take place immediately or soon after the patient consents to the study. The rater will conduct the following assessments: Barthel, 6 minute walk, gait speed, SCID, MADRS, PANAS, Disposition, Clock Drawing Test, Fear of Falling, Readiness for Rehab, CIRS-G, Barthel Index: Pre-morbid version.

F4 Day 7 Visit

The day 7 visit will take place 7 days after the patient consents to the study. The rater will conduct the following assessments: PANAS, Readiness for Rehab.

F5 Day 30 Visit

The day 30 visit will take place 30 days after the patient's date of admission to the facility. If the patient has already been discharged from the skilled nursing facility, the rater will call the patient to schedule a home visit to conduct the following assessments: Barthel, gait speed, MADRS, PANAS, Follow-up Disposition.

F6 SNF Discharge

The discharge visit will take place as close in time to the patient's discharge date as possible. The rater will conduct the following assessments at the skilled nursing facility: Barthel, 6 minute walk, gait speed, Discharge Location..

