
Our sample size is based on 80% power to detect a Cohen's $d=0.4$ effect size on the ANCOVA difference in treatments at day 21, based on a two-tailed $p<0.025$ (because two outcome measures are used). G*Power 3.1.2 was used for power calculations. A Cohen's $d=0.4$ is between "small" (0.2) and "medium" (0.5) effect sizes. Effect sizes for function were in the "large" range, $d=0.7-0.9$, but we acknowledge that these observed

effect sizes are qualified by the small sample size, and it makes most sense to be more cautious regarding likely effect sizes in a full-scale study, hence our choice to power at $d=0.4$. Such an effect size is clinically relevant for the functional outcomes.³ *We will only examine affective recovery as an outcome for those who are “affectively impaired” to begin with; i.e., those with clinical depression at baseline; with this reduced N, we are powered at 80% for a $d=0.54$. This same power analysis would apply for any subgroup analysis of depressed; i.e., if we wish to demonstrate that EMR is effective both in the case of clinical depression and in “non-depressed” older adults.*

G2 Interim Monitoring and Early Stopping

Not applicable; we do not have any interim data analysis or early stopping plans.

G3 Analysis Plan

The continuous demographic and clinical variables at baseline will be compared between the EMR group and the SOC group using the Two Independent Sample t Test or the Wilcoxon Two Sample Test, whichever is appropriate. Baseline categorical variables (e.g., race) will be compared between the groups using either the Chi Square Test or Fisher’s Exact Test, whichever is appropriate. We will examine data descriptively using crosstabulations, histograms, and tests for normality (with corrective actions, data transformation or nonparametric alternatives, as needed). An analysis-appropriate technique will handle missing data.

G4 Statistical Methods

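### The SAP moves the primary time point from Day 30 to discharge but keeps a length-of-stay claim that holds only for a fixed day

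*SAP*

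**What the plan says.** Protocol C1 states "Our primary analysis is the change from baseline to Day 30" and justifies it as an "effectiveness test that is not confounded by length of stay differences or post-discharge issues beyond the reach of EMR". The schedule in protocol F2 marks the Day 30 column as the primary endpoint. Under F5 that visit is counted from the admission date and is made at home if the patient has already left.

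The SAP (Introduction, ii. Objectives, Aim 1) says instead: "Our primary analysis is the change from baseline to Discharge. This single primary endpoint allows for an effectiveness test that is not confounded by", and the sentence then ends exactly as in the protocol, with length-of-stay differences and post-discharge issues. Only the time point has changed; the justification is repeated as it stood. The switch is carried through the rest of the SAP. Its schedule no longer labels Day 30 as primary, and its primary model (Analysis, ii) has baseline and discharge as the two levels of time.

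The discharge visit has no fixed day. Protocol F6 says only "The discharge visit will take place as close in time to the patient's discharge date as possible". A third time point appears in protocol G1, where the sample size rests on "the ANCOVA difference in treatments at day 21". The SAP's sample-size text refers to the primary endpoint without naming a day.

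**The concern.** The protocol's argument for Day 30 has two parts: a fixed day removes the effect of different lengths of stay, and an early day limits what happens after EMR has ended. Only the second part carries over to discharge. The first becomes untrue, because each patient's assessment time is then set by the length of stay.

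This matters because it is the stated basis of the primary test. A reader of the SAP would take the Barthel contrast as protected from length of stay when nothing in the plan protects it. If patients leave on reaching a functional goal, faster recovery shows up partly as a shorter stay rather than a higher discharge score. If one arm stays longer for any other reason, its discharge score includes more days of recovery. The protocol recognises the issue: G4 lists varying length of stay among the reasons why the data to Day 90 may become naturalistic.

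**Working it through.** **Comparison of the texts**

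| Item | Protocol | SAP |
|---|---|---|
| Primary time point | Day 30 from admission (C1, F2, F5) | SNF discharge (Objectives; Analysis ii) |
| Claimed freedom from length-of-stay differences | Yes; fits a fixed day | Yes; does not fit discharge |
| Claimed freedom from post-discharge issues | Yes | Yes; fits discharge |
| Length of stay in the primary model | Not needed at a fixed day | No term |
| Length of stay in exploratory analyses | – | Not listed (age, gender, race, site only) |
| Baseline-to-Day 30 Barthel change | Primary | Not clearly analysed |

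On the last row, the SAP plans a model at 30, 60 and 90 days for an outcome it calls self-reported function. The Barthel is the only function measure scheduled at all three times (the IADL scale is at 60 and 90 only), so it may be what is meant. It is not named, however, and the model has no baseline level, so it is not the protocol's primary contrast.

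**How far stay can matter**

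The documents say only that stay is about 3 weeks. Every other input below is an assumption, used to see whether size and direction can be pinned down.

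*Direct shift.* Shift in d = recovery per day × difference in stay ÷ SD. Assume 0.5 to 1.5 points per day and SD 15 to 25.

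- 3-day difference: smallest 0.5 × 3 ÷ 25 = 0.06; largest 1.5 × 3 ÷ 15 = 0.30.
- 5-day difference: smallest 0.5 × 5 ÷ 25 = 0.10; largest 1.5 × 5 ÷ 15 = 0.50.

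The design effect is d = 0.4, so the range runs from minor to larger than the target.

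*Direction, by simulation.* Assume baseline Barthel with mean 50 and SD 15, recovery with mean 1.0 and SD 0.55 points per day, EMR adding 0.25 per day, scores limited to 0–100, and stay limited to 10–40 days. Goal-driven discharge means leaving at Barthel 80; independent stay has mean 21 and SD 7 days. Here d is the baseline-adjusted difference divided by the residual SD.

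| Discharge rule | EMR gain after discharge | d at Day 30 | d at discharge |
|---|---|---|---|
| Goal-driven | continues | 0.42 | 0.32 |
| Goal-driven | stops | 0.36 | 0.32 |
| Independent of function | continues | 0.42 | 0.36 |
| Independent of function | stops | 0.29 | 0.36 |

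In the goal-driven rows EMR patients leave 3.2 days earlier (25.1 against 28.3 days).

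A second set of assumptions uses baseline mean 45 and SD 15, recovery mean 1.0 and SD 0.4 per day, EMR 30% faster, measurement noise SD 6, and discharge at Barthel 65 or 75 within 7–45 days. With d taken on change scores, it gives about 0.52 at Day 30 and 0.09 to 0.12 at discharge. With no EMR effect and the same discharge process in both arms, both endpoints give 0.

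The gap between the two endpoints therefore runs from large to small, and its sign reverses in the fourth row of the table. The two time points measure different things, and the documents do not say by how much.

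**The case against.** The strongest reply is that discharge is a reasonable primary time point. EMR is delivered in SNF therapy sessions, so discharge is the end of treatment. With a stay of about 3 weeks, Day 30 falls roughly 30 − 21 = 9 days after a typical discharge, and the clause on post-discharge issues fits discharge better than Day 30. Length of stay follows randomisation, so it is not a confounder in the strict sense, and comparing the arms at discharge remains a valid randomised comparison. All of this stands. It defends the choice of discharge, but not the statement that the choice removes length-of-stay differences.

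A reader might infer that the change was made knowing the results. The SAP (version 2, dated 5/29/2019) does report study data: 22 SCID interviews and 14 depression diagnoses. These counts are pooled over arms, and the SCID is scheduled only at baseline. They show that study data were in hand, not that Barthel results by arm had been seen. The proper response is to ask for the date, the reason and the blinding status.

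A reader might also infer that discharge scores will be missing in the sickest patients, because that visit takes place at the SNF. Protocol G4 expects missing data after discharge too, and no procedure is given for a patient who is in hospital on Day 30. The documents do not show which time point would lose more.

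**Conclusion.** The length-of-stay clause in the SAP is wrong as written. It describes a property of Day 30 and is attached to an endpoint that lacks it, with no model term, no planned report of stay by arm and no clearly specified Day 30 Barthel change analysis to make up for it. This rests on the texts alone and needs no assumption.

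Two stronger conclusions are tempting and not supported. One is that the primary test is biased or has lost a stated amount of power: no document shows that stay differed by arm, the inputs needed are absent, and plausible assumptions move the effect either way. The other is that Day 30 must be restored as primary: that would swap exposure to length of stay for exposure to post-discharge events, which is a trade-off for the sponsor.

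**What to change.** 1. In the SAP Objectives, delete the length-of-stay clause. The clause on post-discharge issues may stay. State that the primary estimand is function at discharge.
2. Prespecify baseline-to-Day 30 Barthel change, in the same marginal model, as a named key sensitivity analysis reported beside the primary result. Say which instrument the 30/60/90-day model of self-reported function uses.
3. Report length of stay by arm.
4. State when and why the primary time point changed, and whether outcomes by arm had been seen by then.
5. Reconcile day 21 in protocol G1 with the primary time point.

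Restoring Day 30 as primary is open to the sponsor but is not a required correction. The cost is SAP wording, a one-line protocol clarification, one descriptive summary and one extra model on data already scheduled. The downside is that a discordant Day 30 result, if there is one, would have to be reported.
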